**Study Protocol**

**University Of Pittsburgh IRB STUDY22020096 Approved 4/5/2022**

At Magee, based on medical records, pregnant and postpartum women meeting the study eligibility criteria will be asked to join the study. Following enrollment, mothers will be randomized to one of two groups: FCU-Heart (intervention) or FCU Alone (usual care comparison). The FCU begins with an assessment of parent-child interaction quality, caregiver psychological resources and support, and child risk/promotive factors. FCU assessments are typically one hour in length; using only 30 minutes to complete the FCU alone ecological assessment provides another 30 minutes for evaluating maternal and infant CVH.

**Intervention:** A Family Check-Up family coach will meet with families for a “check-up” about the child’s development and behavior and how to improve their own well-being to support the child’s development. The Family Check-Up typically takes place over the course of 3-5 sessions, each about an hour long. These meetings take place at home or wherever is most convenient including virtually online.

- First, a trained Family Check-Up family coach will conduct an “Initial Interview.” The second step is completing questionnaires about the child and family relationships and social support. An important part of this second step is the family interaction tasks, where mother and child will take part in activities like playing together with toys and puzzles. The Family Check-Up family coach will then highlight parenting strengths during the third meeting, called the Feedback Session.
- Assessments also include measurement of your blood pressure, body mass index, diet quality, exercise, smoking. During the Feedback Session, the Family Check-Up family coach will meet with you for a conversation about strengths and challenges for your child and family as a whole. You’ll be invited to set goals for you and your child to support and maintain strengths, and to address any areas of concern.
- After the Feedback Session families have the option to continue meeting with your family coach to support the child’s development and improve parental well-being.

Participants randomly selected to participate in the Family Check-Up Heart program will also receive information about healthy eating and weight loss, stress management, and smoking and to monitor weight and blood pressure. ENRICH foundational modules will be incorporated as appropriate.

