**Maternal CVH:** BP and BMI will be assessed using validated Bluetooth devices and following standardized research protocols. Diet quality will be assessed using the Rapid

Eating Assessment for Participants (REAP-S). Physical activity in mothers will be assessed using (1) the Pregnancy physical activity questionnaire (PPAQ), which measures active and sedentary behavior and (2) bluetooth data from Fitbit devices using standardized research protocols. Smoking will be assessed via questionnaire. These measures allow feedback by the family coaches.

The blood pressure and weight data measured by the iHealth devices is transmitted via Bluetooth to the participant's personal device and loaded into the installed iHealth app. From there, the iHealth app securely transmits the BP data to the participant's iHealth cloud account. Our team will make API requests to download the data from the iHealth cloud to a secure UPMC server and upload it to a REDCap database. The same process will be used to collect Fitbit activity data from the Fitbit app and cloud account. Data transfer over the internet using either the iHealth Cloud API, the Fitbit API, or the REDCap API is secure and encrypted (using the HTTPS protocol). The iHealth and Fitbit cloud data access are authorized at the time of recruitment and are valid for one year. The participant is also able to revoke the access anytime in her iHealth cloud account or the Fitbit cloud account.

Outcomes CVH assessments at 6 months will be conducted remotely when possible for the FCU Alone control group. Control group participants will be sent a body weight scale and BP cuff when they are due for their 6 month measurements. After they receive them, staff will facilitate the measurements virtually and let them keep the devices. We will do in person assessments only as needed, and will provide the scales and BP cuffs to keep at study conclusion.

All participants will be given a handout from NHLBI (uploaded in local supporting documents section) at the study conclusion after they complete the 6-month outcomes assessment. They will also be provided with the American Heart Association's web page that addresses understanding blood pressure readings. If the outcome readings are elevated or high, they will also be advised to consult with their doctor.

Child CVH will be assessed with BP and BMI. BP will be measured following a standardized research protocol using a pediatric-sized cuff.

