**Expanding the Family Check-Up in Early Childhood to Promote Cardiovascular Health
of Mothers and Young Children (NCT05473767)**

Data Analysis Plan

University Of Pittsburgh IRB STUDY22020096 Approved 4/5/2022

As it is a pilot study, the focus will be on the estimation of the difference in mean levels of blood pressure and weight between women in FCU-Heart and FCU alone. Let δ be the intervention effect, representing the difference in mean BP and weight at 6 months between the two intervention arms. The mean difference δ will be estimated first by separately estimating the group means using observed sample means, and then taking a difference of the observed sample means. We will use two-sample t-distribution to construct a 95% confidence interval of the estimated δ to quantify the uncertainty in the estimation. The analysis will be repeated for each race stratum. With 100 participants in FCU-Heart and 50 in the standard FCU group, we will be able to estimate δ with a margin of error of 13.7% with 95% confidence, assuming a standard deviation of 40% in both populations. The sample sizes are sufficient to detect an effect size of 0.5 with 82% power at 5% level of significance. An effect size of 0.5 is consistent with intervention effects from the first early childhood FCU RCT on both parenting ($d=.48$) and child problem behavior ($d=.64$) 1-2 years post-intervention. Based on attaining 90% retention for the 6-month follow-up of the TPS-FCU study and our CVH intervention, we expect that our retention will also be ~90%. All the analyses will follow intention-to-treat principle (analyzed as randomized).

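### δ is estimated without the entry BP and weight that the FCU assessment appears to collect; the estimate is valid, but if both arms have a comparable entry reading, precision is being given up

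*SAP*

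**What the plan says.** **SAP, Data Analysis Plan.** The stated focus of this pilot is estimation of δ for BP and weight at 6 months. The estimate is to be "estimated first by separately estimating the group means using observed sample means, and then taking a difference of the observed sample means", with a 95% interval from the two-sample t distribution, and the analysis is repeated by race. No baseline value, covariate or change score is named. The precision statement is a margin of 13.7% for 100 vs 50 women with an SD of 40%, and 82% power for an effect size of 0.5. Retention is expected to be about 90%.

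**Protocol, pointing towards an entry reading in both arms.** The opening paragraph of the Study Protocol explains that "using only 30 minutes to complete the FCU alone ecological assessment provides another 30 minutes for evaluating maternal and infant CVH". Under Intervention, in the general description that comes before the extras for FCU-Heart women, it says: "Assessments also include measurement of your blood pressure, body mass index, diet quality, exercise, smoking". Under Implementation measures, controls found to have raised BP are mentioned just after the sentence on communicating findings from the FCU.

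**Protocol, pointing the other way.** Under Maternal CVH, "Control group participants will be sent a body weight scale and BP cuff when they are due for their 6 month measurements". The same section says of the maternal CVH measures: "These measures allow feedback by the family coaches". It also says of the 6-month results: "If the outcome readings are elevated or high, they will also be advised to consult with their doctor". The mention of controls with raised BP, which carries no time point, could therefore refer to 6 months.

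**Order and population.** "Following enrollment, mothers will be randomized to one of two groups", and the assessment is described after that. Entry is mixed: "pregnant and postpartum women meeting the study eligibility criteria will be asked to join the study".

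**The concern.** When the deliverable is an interval for δ, its width is what the trial buys. A woman's BP or weight at entry usually predicts the same measure six months later. In a randomized comparison, a linear model that includes the entry value removes about r² of the outcome variance from the error term, so the interval shrinks by a factor of about √(1 − r²) with no extra recruitment. If the FCU assessment yields that value in both arms, the planned estimator leaves it unused.

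The choice is also best made now. If entry values exist and the SAP is silent, a raw and an adjusted result will both be available later, with nothing to say which is primary.

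**Working it through.** **1. Reproduce the SAP's figures (unadjusted, 100 vs 50).**
Margin in SD units = t(0.975, n1+n0−2) × √(1/n1 + 1/n0).
- 1.976 × √(1/100 + 1/50) = 1.976 × 0.1732 = 0.342 SD. Times 40% this is 13.7%, as stated.
- Two-sided power for an effect size of 0.5 is 81.8% by noncentral t and 82.3% by the normal approximation, which agrees with the stated 82%.

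**2. The raw analysis at the SAP's expected retention.** With 90% retained in each arm (equal retention is an assumption), 90 vs 45 are analysed.
- 1.978 × √(1/90 + 1/45) = 1.978 × 0.1826 = 0.361 SD (14.4% on the 40% SD). Power is 77.6%.
- This widening comes from attrition, not from leaving out baseline. It serves here only as the reference for step 3.

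**3. The entry-adjusted analysis, 90 vs 45.** The model is 6-month value on arm and entry value, with ordinary standard errors and N = 135.
Margin = t(0.975, N−3) × √(1/n1 + 1/n0) × √(1 − r²) × √(1 + 1/(N−4)). The last factor allows for chance imbalance in the covariate.
At r = 0: 1.978 × 0.1826 × √(1 + 1/131) = 0.3625. Other rows multiply this by √(1 − r²).

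| r (assumed) | Closed form, SD | Simulated mean, SD | Change from raw 0.361 (closed form) | Power at effect size 0.5 |
|---|---|---|---|---|
| 0 | 0.3625 | 0.362 | 0.4% wider | 77.3% |
| 0.2 | 0.355 | 0.354 | 1.6% narrower | 78.9% |
| 0.3 | 0.346 | 0.345 | 4.2% narrower | 81.0% |
| 0.5 | 0.314 | 0.314 | 13.1% narrower | 87.8% |
| 0.7 | 0.259 | 0.258 | 28.3% narrower | 96.7% |

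Closed form and simulation agree to about 0.001 SD. Adjustment breaks even with the raw analysis at r of about 0.09. SD units are the safer scale, because the SAP does not say what BP or weight quantity its 40% SD is a percentage of.

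**4. Race strata.** The documents give no stratum sizes. At r = 0.3 the same model against the raw difference gives 0.498 vs 0.518 SD at 45/22, 0.614 vs 0.636 at 30/15 and 0.764 vs 0.786 at 20/10. The interval narrows on average in all three.

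**5. A heavier model.** Adding pregnant/postpartum status and HC3 standard errors gives 0.369, 0.362, 0.352, 0.320 and 0.263 SD at r = 0, 0.2, 0.3, 0.5 and 0.7. The gain at r = 0.2 then disappears, but that is the price of the additions, not of adjusting for baseline.

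**6. Missing entry values (run in the heavier model).** With 10% missing at random and replaced by the pooled mean, the margins are 0.354, 0.325 and 0.275 SD at r = 0.3, 0.5 and 0.7, with coverage about 95%. If missingness in controls depends strongly on the value (assumed: low values nine times as likely to be missing as high), 5% vs 10% missing by arm biases δ by 0.02 to 0.05 SD over those r. With 5% vs 40% missing the bias is 0.09 to 0.21 SD. Imputation is therefore suitable only when few entry values are missing in either arm.

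**The case against.** **Nothing in the plan is wrong.** This stands. A difference in means with a t interval is unbiased under randomization, and the SAP's 13.7% and 82% both reproduce. A reader might infer that omitting baseline biases δ or invalidates its interval; it does neither. Nor is chance imbalance at entry a separate harm, since it is the same r² already counted in the precision gain.

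**The control baseline is unconfirmed.** This stands too. A reader might infer that the SAP discards a reading both arms are known to have. No section says so: controls receive their devices only for the 6-month measurement, and the mention of raised BP in controls has no time attached. The recommendation must depend on a check.

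**The reading follows randomization and the coach's initial interview.** True, and a rule requiring a reading before any contact at all would exclude it. But the interview and assessment are described as common to both arms. What matters is that the reading comes before the Feedback Session and any FCU-Heart content.

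**r is unknown and may be low.** Mixed pregnant and postpartum entry may weaken it, especially for weight. In the heavier model, with half the women pregnant at entry, correlations of 0 (pregnant) and 0.5 (postpartum) give 0.357 SD, and 0.1 and 0.3 give 0.362, which is little or no gain. This limits the benefit, but the cost of adjusting when r is zero is 0.362 against 0.361 SD.

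**Adjustment does not repair attrition.** A reader might present it as restoring the quoted 13.7%. The move from 13.7% to 14.4% comes from retention and is a separate matter.

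**Conclusion.** The point holds as a conditional precision improvement, not as an error. The planned estimator uses no entry value although the Protocol suggests that one is collected. If both arms have a comparable reading, the 95% margin at 90 vs 45 falls from 0.361 SD by very little at r = 0.2, by about 4% at r = 0.3, 13% at r = 0.5 and 28% at r = 0.7. At r = 0 nothing is gained and practically nothing lost.

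This rests on an assumed range for r, on 90% retention in each arm, on equal SDs in the two arms (as the SAP assumes), and on an entry reading in controls that the documents suggest but do not confirm. Because the trial's aim is estimation and the change is nearly free, it is worth making. If the reading is absent or not comparable, the planned analysis should stand.

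**What to change.** 1. Before any 6-month outcome is seen, confirm for BP and weight separately that both arms have an entry reading taken at the shared FCU assessment, before the Feedback Session and any FCU-Heart content, and by a comparable method. Report missing counts by arm.
2. If so, make the primary estimate the arm coefficient with its 95% CI from a linear model of the 6-month value on arm and the entry value of the same measure. Keep every randomized woman with a 6-month value, replacing the few missing entry values by the mean pooled over both arms. Report the raw difference as supporting.
3. If not, keep the raw difference as primary and say why. Do not fill in entry readings in one arm only.
4. HC3 standard errors, a pregnant/postpartum term and a minimum stratum size for adjustment by race are optional and not needed for the gain.

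Cost: a few lines of SAP wording, one check of baseline availability and one regression per outcome. No new data collection.

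### δ is the unadjusted difference of observed 6-month means, so about 15 of 150 randomised women contribute nothing to it, and no missing-data assumption or sensitivity analysis is stated

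*SAP*

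**What the plan says.** The SAP (Data Analysis Plan) defines δ as "representing the difference in mean BP and weight at 6 months between the two intervention arms". It is to be obtained by "separately estimating the group means using observed sample means, and then taking a difference of the observed sample means", with a 95% confidence interval from the two-sample t distribution, and the analysis is repeated within each race stratum. No baseline adjustment is mentioned.

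On follow-up the SAP says "we expect that our retention will also be ~90" per cent. On the analysis population it says "All the analyses will follow intention-to-treat principle (analyzed as randomized"), so the parenthesis defines intention-to-treat as keeping women in the arm to which they were allocated.

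The protocol adds two relevant facts:

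- **Maternal CVH:** "Control group participants will be sent a body weight scale and BP cuff when they are due for their 6 month measurements". Staff then guide the measurement remotely, in-person assessment is available where needed, and the women keep the devices. No matching description is given of how the 6-month outcome is obtained in FCU-Heart.
- **End of the Implementation measures text:** a participant who loses her pregnancy or infant is withdrawn. The SAP does not say how she enters δ.

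Neither document mentions imputation, a likelihood-based model, an assumption about why values are missing, or a sensitivity analysis.

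**The concern.** As a pilot, the trial has the estimate of δ and its interval as its main product. An estimator built on observed means silently drops every woman without a 6-month value. If those women differ from the measured ones, and either the amount of loss or the size of that difference is not the same in both arms, δ is shifted. The t interval reflects sampling error only and would not show the shift.

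The 90% retention target gives no protection, because it is an overall figure that very different losses by arm can satisfy. The protocol gives a reason why the arms could differ. A control's 6-month value depends on a delivery and a facilitated session at that point, whereas FCU-Heart women are told to monitor weight and blood pressure during the programme. The analysis by race stratum rests on fewer women, so each missing value counts for more there.

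**Working it through.** **Inputs from the SAP.** Arms: "With 100 participants in FCU-Heart and 50 in the standard FCU group". Spread: "assuming a standard deviation of 40% in both populations". Stated precision: "margin of error of 13.7% with 95% confidence". Planning effect: 0.5 SD, with 82% power at the 5% level. Expected retention: about 90%.

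**Step 1: reproduce the plan's figures.**

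- Half-width = t(0.975; n1+n2−2) × SD × √(1/n1 + 1/n2).
- With 100 and 50 women: 1.976 × 40 × √(1/100 + 1/50) = 1.976 × 40 × 0.1732 = 13.69%. This matches 13.7%.
- Two-sided power at 0.5 SD is 82.3% (normal) or 81.8% (noncentral t). This matches 82%.

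Both stated figures therefore use all 150 women, before any loss.

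**Step 2: how many women the estimator uses.** 10% of 150 = 15 women without a 6-month value. If loss is equal by arm, 90 and 45 remain. The half-width is then 1.978 × 40 × √(1/90 + 1/45) = 14.4% (0.361 SD), and power is about 78%. This step concerns precision only, not bias.

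**Step 3: bias of the observed-mean difference.** Let m be the share missing in an arm and g the observed mean minus the missing mean, in SD units. The mean over all women in the arm is (1−m) × observed + m × missing, so the observed mean is off by m × g. For δ = FCU-Heart minus FCU alone:

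bias = m1 × g1 − m2 × g2.

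The documents give neither m by arm nor g, so every row below is an assumption. A negative g means that missing women have higher (worse) values.

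| Loss FCU-Heart / control | g1, g2 | Bias in δ (SD) |
|---|---|---|
| 10% / 10% | equal in both arms | 0 |
| 10% / 10% | −0.5, 0 | −0.05 |
| 10% / 10% | −0.5, +0.5 | −0.10 |
| 10% / 10% | −1, +1 | −0.20 |
| 5% / 20% | −0.5, −0.5 | +0.075 |
| 5% / 20% | −1, −1 | +0.15 |
| 15% / 0% | −0.5 | −0.075 |

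The 5%/20% split is consistent with the retention target: 5 + 10 = 15 of 150 women. Its bias is (0.20 − 0.05) × 0.5 = 0.075 SD and (0.20 − 0.05) × 1 = 0.15 SD. On the SAP's scale (SD 40%) that is 3 and 6 percentage points.

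**Step 4: put the bias in proportion.** The 5%/20% split leaves 95 and 40 women. The half-width is 1.978 × √(1/95 + 1/40) = 1.978 × 0.1885 = 0.373 SD.

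- Bias relative to half-width: 0.075/0.373 = 20%; 0.15/0.373 = 40%.
- Bias relative to the planning effect: 0.075/0.5 = 15%; 0.15/0.5 = 30%.
- Bias relative to the standard error: 0.075/0.1885 = 0.40; 0.15/0.1885 = 0.80. If the observed values are roughly normal with SD 1, a nominal 95% interval would then cover the true δ about 93% and 88% of the time.

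**The case against.** The strongest reply is that this is a small pilot aimed at estimation, that about 10% loss is modest, and that the bias may be zero. Two observed means are easy to read, and in each scenario of the table the bias stays below the interval half-width. All of that stands, and it limits the weight of the point.

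Three stronger readings are tempting, and the documents do not support them.

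- **That the plan breaks its own intention-to-treat commitment.** The SAP defines the term as analysis by assigned arm, and observed means by assigned arm meet that definition. It does not promise a value for every randomised woman.
- **That the estimate is valid only if values are missing completely at random.** The first row of the table shows otherwise: equal loss with equal departures gives no bias. Nor is there bias if missingness depends on arm alone.
- **That loss is likely to be higher in controls.** The SAP gives one retention figure, not split by arm. The protocol supports control follow-up with remote facilitation, devices to keep and an in-person fallback. It does not say that FCU-Heart outcomes are taken from transmitted data without a 6-month assessment. Unequal loss is possible, in either direction.

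It is also fair to say that imputation or modelling removes only the part of the bias that the predictors explain, so the figures above are not what the fix would gain. Interim device data may exist mainly in FCU-Heart, so a model leaning on them could use unequal information by arm. The fix has to respect both limits.

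**Conclusion.** The point holds as a gap in the analysis plan with a cheap improvement available. The estimator is explicit, the expected loss is the SAP's own, and nothing in either document says what is assumed about the roughly 15 women who would be left out.

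Whether δ would in fact be biased, by how much and in which direction cannot be determined from the documents. Under the assumed scenarios in the table the size runs from 0 to 0.20 SD, and for the 5%/20% split from 0.075 to 0.15 SD. The conclusion that the estimator omits these women needs no assumption beyond 90% retention. The size rests wholly on the assumed loss by arm and on the assumed gap between missing and observed women.

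**What to change.** Amend the SAP as follows.

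1. **Main estimate.** State a missing-at-random assumption. Estimate δ with a baseline-adjusted likelihood model or with multiple imputation carried out separately by arm.
2. **Predictors.** Use only variables available in both arms: baseline study or medical-record blood pressure or weight, race, and pregnancy or postpartum status. The documents give no measurement schedule by arm, so confirm first which baseline values exist for controls. Access to medical records is requested from all participants and may fill gaps.
3. **Withdrawals.** Say separately how women withdrawn after pregnancy or infant loss enter the estimand. Imputing a 6-month value for them is a question of what δ means, and a general imputation model should not settle it by default.
4. **Attrition.** Report the number and share without a 6-month value by arm, with reasons.
5. **Sensitivity analysis.** Show δ and its interval over a stated range of shifts applied to the missing values separately by arm. A displayed range suits an estimation pilot better than a search for the point at which a conclusion changes, since the SAP states no decision rule.
6. **Description.** Keep the observed means and their difference as a descriptive table.

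The cost is SAP wording, slightly more analysis and a less simple presentation than two raw means. No new data collection is needed if usable baseline or medical-record values exist in both arms.

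### The overall δ is valid but makes no use of the race strata in the SAP; a race term would keep it consistent with the stratum results at almost no cost

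*SAP*

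**What the plan says.** The SAP (Data Analysis Plan) obtains δ for blood pressure and weight at 6 months by computing each arm's mean separately and "then taking a difference of the observed sample means". For the interval it states: "We will use two-sample t-distribution to construct a 95% confidence interval of the estimated δ". On race it says only: "The analysis will be repeated for each race stratum".

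No race term, stratified combination or other covariate adjustment appears in either document. The protocol's opening paragraph says that mothers are randomised to one of two groups and does not mention stratification by race. The planned sizes are given as "With 100 participants in FCU-Heart and 50 in the standard FCU group".

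**The concern.** The stratum analyses require a race category for each woman, yet the overall estimate leaves that information out. If one arm happens to contain more women of a race with higher blood pressure or weight, the imbalance moves the overall estimate but moves neither race-specific estimate. The overall figure is then not an average of the stratum figures printed beside it, and it can lie outside all of them.

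Two things are at stake: whether the overall and stratum results agree with each other in the report, and a small amount of precision in the main interval. The SAP describes the study as a pilot whose focus is estimation, so the estimates are its main product.

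**Working it through.** **1. The SAP's own figures.** Inputs from the SAP: 100 and 50 women, "assuming a standard deviation of 40% in both populations", 5% significance level, effect size 0.5.

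- Margin of error = t(0.975, 148) × 40 × √(1/100 + 1/50) = 13.69, which matches the stated "margin of error of 13.7% with 95% confidence".
- Two-sided power at effect size 0.5 is 82.3% (normal) or 81.8% (noncentral t), which matches the stated 82%.

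Both figures therefore describe the unadjusted comparison. In SD units the standard error of δ is √(1/100 + 1/50) = 0.173.

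**2. How race enters the raw estimate.** Take two strata with stratum differences D1 and D0. Let pT and pC be the shares of race 1 in FCU-Heart and FCU Alone, and let C1 and C0 be the control means by race. Then

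raw δ = pT·D1 + (1 − pT)·D0 + (pT − pC)·(C1 − C0).

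The first two terms are a weighted average of the stratum differences. The third is the race imbalance multiplied by the race difference among controls. It appears in neither stratum result.

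*Illustration with assumed values.* Control means are 122 and 116 mmHg, the effect is −3 mmHg in both strata, and race 1 makes up 50 of 100 in FCU-Heart and 17 of 50 in FCU Alone.

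- FCU-Heart mean: 0.50 × 119 + 0.50 × 113 = 116.00.
- FCU Alone mean: 0.34 × 122 + 0.66 × 116 = 118.04.
- Raw δ = −2.04, although each stratum shows −3.0. Check: −3 + 0.16 × 6 = −2.04.

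The 16-point imbalance used here is large, close to the 95% limit in step 3.

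**3. Likely size of the imbalance.** Assume simple 2:1 randomisation with a share p in one stratum. The SD of pT − pC is √(p(1 − p) × 0.03), which is 0.079 at p = 0.3 and 0.087 at p = 0.5. The 95% limit is about 0.16 to 0.17. Multiplying by race differences of 0.2, 0.4 and 0.6 SD gives shifts in the estimate of at most about 0.03, 0.07 and 0.10 SD in 95% of trials.

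**4. How often the overall estimate falls outside both strata.** Results from simulated trials at 100 and 50 women (20,000 to 40,000 per setting for the rates), two strata, p = 0.3 to 0.5, race difference in units of the within-race SD:

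| Race difference | Raw δ outside both strata | Median overshoot | Overshoot above 0.05 SD |
|---|---|---|---|
| 0.2 SD | about 7% | 0.011 SD | about 0.4% |
| 0.4 SD | 12-13% | 0.018 SD | about 1.6% |
| 0.6 SD | about 18% | 0.027 SD | 4-5% |

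At 90 and 45 women, which is the 90% retention the SAP expects, the rates are nearly the same. Coverage of the raw 95% interval was 94.7-95.2%.

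**5. With race in the model.** The arm coefficient from a linear model with arm and race is (w1·D1 + w0·D0)/(w1 + w0), where each w = 1/(1/nT + 1/nC) within the stratum. The weights are positive, so the estimate always lies between D1 and D0. In the illustration it is −3.0.

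**6. Precision.** The share of variance explained by race is R² = g²p(1 − p)/(1 + g²p(1 − p)), where g is the race difference, and the ideal narrowing is 1 − √(1 − R²). Estimating the race term costs about 1/(2 × 149) = 0.34% in standard error (simulated: about 0.35%).

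| g | Ideal narrowing | Realised narrowing (simulated) | Margin, from 13.69 |
|---|---|---|---|
| 0.2 | 0.4-0.5% | about 0.1% | 13.68 |
| 0.4 | 1.6-1.9% | 1.3-1.6% | 13.47-13.51 |
| 0.6 | 3.6-4.2% | 3.3-3.9% | 13.16-13.24 |

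The last column is 13.69 × (1 − realised narrowing).

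**The case against.** The strongest reply is that nothing is wrong. Under randomisation the raw difference is unbiased, and its t interval already allows for chance imbalance in race. This stands, and the simulated coverage confirms it. A reader might infer from the imbalance argument that δ is biased or its interval invalid. The documents do not support that: the noise is in the estimate, and the interval accounts for it.

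A reader might also infer that an overall estimate outside the stratum estimates could not be interpreted. That is too strong. It happens mainly when the stratum estimates almost coincide: in those trials the median gap between them is 0.02-0.06 SD, against about 0.25 SD in all trials. Readers would see three similar numbers with wide intervals, which is awkward to explain but not meaningless.

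It is also fair to say that every size here rests on assumptions, since the documents give no race categories, race mix or race difference in outcome. If randomisation is stratified by race, the imbalance is near zero at entry; simulation then put the overall estimate outside both strata in 0-4% of trials after dropout. A reader might go further and say that the SAP ignores a stratified design. The documents never say that the design is stratified.

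Finally, the protocol does not describe collecting race; the SAP only implies it by planning stratum analyses. This also stands, so the fix should name the categories.

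**Conclusion.** The planned overall analysis is valid, and this point is a low-priority refinement. Under the assumptions stated (two strata, 30-50% in one, simple 2:1 randomisation, race differences of 0.2-0.6 SD), the overall estimate falls outside the race-specific ones in about 7-18% of trials, usually by a trivial amount. Race adjustment removes that possibility and narrows the interval by about 0.1-4%.

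The case rests mainly on agreement between the overall and stratum results, since the gain in precision is modest. The change helps whichever way randomisation was done. If it is unstratified, the gain is agreement plus a little precision; if it is stratified by race, the gain is a slightly narrower interval that matches the design. No conclusion of the pilot is likely to depend on it.

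**What to change.** In the SAP:

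- Estimate the overall δ and its 95% interval, for each outcome, from a linear model with arm and race stratum.
- Name the race categories and their source. Use the same categories here and in the stratum analyses, with sparse categories pooled by a rule fixed in advance.
- Keep the raw difference and its two-sample t interval as a supporting figure, so that the stated 13.7% margin still has its counterpart in the report.
- State whether randomisation is stratified by race.

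The cost is a few sentences in the SAP, one degree of freedom per extra race category, and about 0.35% in precision if race turns out to be unrelated to outcome. It needs no extra participants or visits, and no data beyond what the stratum analyses already require.

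### If 100 and 50 are enrolled numbers, the stated 82% power and 13.7% margin ignore the SAP's own ~90% retention; with equal loss per arm they become about 78% and 14.4%

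*SAP*

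**What the plan says.** The SAP is a single paragraph headed Data Analysis Plan. On this point it says the following.

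- Purpose: "As it is a pilot study, the focus will be on the estimation" of the difference in mean blood pressure and weight at 6 months.
- Estimator: "separately estimating the group means using observed sample means, and then taking a difference of the observed sample means", with a 95% interval from the two-sample t-distribution.
- Numbers and precision: "With 100 participants in FCU-Heart and 50 in the standard FCU group", the team expects to "estimate δ with a margin of error of 13.7% with 95% confidence, assuming a standard deviation of 40% in both populations".
- Power: "The sample sizes are sufficient to detect an effect size of 0.5 with 82% power at 5% level of significance".
- Retention, two sentences after the power statement: "we expect that our retention will also be ~90" per cent, based on 6-month retention in earlier work.
- Analysis set: intention-to-treat, with women counted in the arm to which they were randomised.

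The SAP does not say whether 100 and 50 are women enrolled or women analysed. The Protocol gives no sample size. Neither document describes imputation or any other way of handling a missing 6-month value.

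**The concern.** The precision and power are quoted for 100 and 50 women, yet the same paragraph expects about one woman in ten to have no 6-month outcome. Under the stated estimator such a woman adds nothing to either group mean. The intention-to-treat statement does not change this: it fixes the arm in which a woman is counted but does not supply a missing outcome. The Protocol also foresees some loss, since a participant who loses her pregnancy or infant is withdrawn.

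If 100 and 50 are enrolled numbers, the SAP therefore claims more precision and power than the sample it expects to analyse can give. Because the stated focus is estimation, the margin of error is the main design figure, so the discrepancy is not confined to a secondary power statement. If they are analysed numbers, the figures are right but a reader cannot tell how many women are to be enrolled.

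**Working it through.** **Inputs, all from the SAP's Data Analysis Plan:** n1 = 100 and n2 = 50; effect size d = 0.5; significance level 5%; SD 40% in both arms; 95% confidence; retention about 90%. Sidedness is not stated. Two-sided is assumed because it reproduces the stated 82%, whereas a one-sided test gives 89%.

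**Formulas**

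- Margin = t(0.975, n1 + n2 − 2) × 40 × √(1/n1 + 1/n2).
- Power: two-sided two-sample t-test from the noncentral t-distribution, with noncentrality d / √(1/n1 + 1/n2) and n1 + n2 − 2 degrees of freedom.

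**Step 1: the SAP's own figures (100 and 50)**

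- √(1/100 + 1/50) = 0.1732.
- Margin = 1.976 × 40 × 0.1732 = 13.69%, or 0.342 SD. Stated: 13.7%.
- Noncentrality = 0.5 / 0.1732 = 2.887; power = 81.8% (normal approximation 82.3%). Stated: 82%.

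Both figures reproduce with no loss to follow-up.

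**Step 2: 90% retention, equal loss per arm (90 and 45)**

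- √(1/90 + 1/45) = 0.1826.
- Margin = 1.978 × 40 × 0.1826 = 14.44%, or 0.361 SD.
- Noncentrality = 0.5 / 0.1826 = 2.739; power = 77.6% (normal approximation 78.2%).
- The effect size detectable with 80% power moves from 0.488 to 0.515.

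**Step 3: sensitivity.** The documents give no loss by arm, and the 90% is approximate.

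| Women analysed (FCU-Heart / FCU Alone) | Power at d = 0.5 | Margin |
|---|---|---|
| 100 / 50 (no loss) | 81.8% | 13.69% |
| 95% retained, equal loss | 79.8% | 14.05% |
| 90 / 45 (90%, equal loss) | 77.6% | 14.44% |
| 85% retained, equal loss | 75.2% | 14.87% |
| 85 / 50 (all 15 lost from FCU-Heart) | 79.5% | 14.10% |
| 100 / 35 (all 15 lost from FCU Alone) | 71.5% | 15.54% |

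The last two rows are bounds for 15 losses, not forecasts.

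**Step 4: the other reading.** If 100 and 50 are to be analysed, enrolment at 90% retention is 100 / 0.9 = 111.1, rounded up to 112, and 50 / 0.9 = 55.6, rounded up to 56, giving 168 in total.

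**The case against.** The strongest reply is that no stated figure is miscalculated. Both follow exactly from their inputs, and if 100 and 50 are completers they need no change. The retention sentence could be there to show that 100 and 50 completers are attainable, and no enrolment total in the Protocol settles the matter. This is fair, and it is why the conclusion is conditional. The enrolled reading remains more natural, because the SAP speaks of participants in each group and then forecasts retention separately, with no inflated target. On either reading something is missing: the attrition allowance, or the label and the enrolment target.

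A second reply is that the effect is small for a pilot. Equal loss costs about 4 points of power and 0.75 points of margin. The effect size of 0.5 is itself supported by earlier effects on parenting and child behaviour, not on blood pressure or weight, so it is far more uncertain than a shift of 0.03. This also stands, and it limits how much weight the point should carry. It does not remove the mismatch, because the margin, which matters most in an estimation study, is affected as well.

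A third reply is that losing 15 women from one arm alone has no basis in the documents. That is correct. Those rows only bound the result, and the conclusion does not rest on them.

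**Conclusion.** The concern holds. The 82% and 13.7% are figures for complete follow-up, while the SAP expects about 90% retention and describes no way for a woman without a 6-month value to contribute. If 100 and 50 are enrolled and loss is equal by arm, power at an effect size of 0.5 is about 78% rather than 82%, and the margin is 14.4% (0.36 SD) rather than 13.7% (0.34 SD). With 15 losses split in any way between the arms, power lies between 71.5% and 79.5% and the margin between 14.1% and 15.5%.

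This rests on three assumptions: that 100 and 50 are enrolled numbers, that the test is two-sided, and, for the central figures, that loss is equal by arm. If 100 and 50 are analysed numbers, the stated figures stand and the gap is the missing label and enrolment target. The final confidence interval will reflect whatever sample is obtained, so its validity is not in question on this point.

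**What to change.** State whether 100 and 50 are enrolled or analysed numbers, then do one of the following.

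- **If enrolled**, restate the precision and power sentences along these lines: *With 90% retention (about 90 FCU-Heart and 45 FCU Alone), the margin of error is 14.4% (0.36 SD), with 78% power for an effect size of 0.5, or 80% power for 0.52.* This needs no extra recruitment. The only cost is slightly less favourable planning figures.
- **If analysed**, label them so, keep 82% and 13.7%, and add the enrolment target: about 112 and 56, or 168 women, at 90% retention.

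Either change is a sentence or two in the SAP. How women without a 6-month value are handled under intention-to-treat is a separate matter that this edit does not settle.
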